Aim 1: We calculated statistical power for the target sample size of 675, with approximately 337 participants enrolled into both TEAM and TECH. After adjusting for the multiple testing in Aim 1 (2 tests) and considering 25% attrition, a sample size of 505 (approximately 252 per treatment group) will provide over 99.9% power for the hypothesis test for Aim 1. Among patients enrolled in the specialty medical home at that time who met active behavioral criteria (PHQ-4 >= 6), there was a significantly greater change in TECH (n=73; ES .49) versus TEAM (n=106; ES .36) for the behavioral composite but both approaches were associated with significant change over time (p=.005). Both approaches were also associated with significant improvement in the biological composite for both TEAM (ES .22) and TECH (ES .16). With the IBD SMH models of care being clinically operational at all three sites, we are collecting ongoing useful and robust information that has been published. In our most recent analyses of our clinical research registry tracking our TEAM approach (n=280), our most recent analyses show effect sizes comparable to these initial findings for both approaches.

Aim 2: We considered both subgroup analyses and formal tests of moderation. Subgroup analyses – Based on current data, our subgroups are relatively evenly proportioned. We expect that the smallest subgroup will be 42% of the sample and the largest will be 58% of the sample. Thus, our expected subgroup sizes after 25% attrition are between 212 and 293 for projected enrollment. For this range of subgroup Ns, we expect 0.80 power to detect small treatment effects ranging between 0.26 and 0.30. Moderation – We used Monte Carlo methods (100 runs) to simulate the binary moderator (M) and treatment (X) (both p=0.5), assuming M independent of X as expected in a randomized trial. Considering a range of effect sizes for B1, B2, and B3, we estimated the outcome Y as Y=B1\*X+B2\*M+B3\*X\*M+ $\varepsilon$ , where  $\varepsilon$ ^N(0,1). We averaged across

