scenarios to determine the typical effect of B3 that can be detected with our current and projected sample sizes after 25% attrition. B3 can be interpreted as the difference between the treatment effect size among those with M=0 (D0=B1). With our projected sample sizes (N=505 after 25% attrition), we expect 0.80 power to detect a significant interaction when the magnitude of B3 is at least 0.50. To provide context for these effect sizes, we note that a B3 of 0.50 could correspond, for example, to a moderate effect of X in one subgroup (e.g., D1=0.60) and a small effect of X in the other subgroup (e.g., D0=0.10).

Our sample size calculations are consistent with the literature for both TEAM and TECH for behavioral and physical disease severity outcomes and there is literature supporting engagement and better outcomes with TECH approach with the younger cohort and those with higher eHealth-literacy. However, the research proposed will be beneficial even if we do not prove our hypotheses. For example, even if TEAM and TECH do not differ in Aim 1, the results can still suggest that TECH is feasible and allows TEAM to be utilized more efficiently. In Aim 2, even if we do not show a strong differential impact of the interventions based on IBD activity, we will still learn valuable information about which subgroups of behaviorally complex IBD patients have highest engagement and impact with each approach.

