#### **Quantitative Analysis**

We will conduct descriptive analyses and multivariate modeling of data to examine changes in outcomes over time and explore moderating variables. All analyses will be intent to treat and conducted as described in our analytic plan and associated protocol. If diagnostic or sensitivity analyses dictate changes to those plans, we will clearly identify subsequent analyses as ad hoc or otherwise deviating from an a priori plan, including labeling subgroup and interaction analyses as confirmatory, exploratory, or post hoc. Our statistician will remain masked to study arm to reduce bias.

Prior to hypothesis testing for Aims 1 and 2, data will be explored by descriptive data analysis. Summary statistics including means, standard deviations, medians, and ranges for continuous variables, or frequencies and percentages for categorical variables, will be presented for the entire sample and stratified by approach at each time point. We will assess the balance of key covariates by visually assessing the standardized differences. We will conduct baseline data analysis for each outcome to explore any pre-intervention differences in outcomes between TEAM and TECH at baseline. Two-sided Wald T-test or Wald F-test using the generalized linear mixed models (GLMMs) with normally distributed random effects for three sites will be used. This estimating method using GLMMs will produce consistent estimations of the regression parameters under the missing at random (MAR) or missing completely at random (MCAR) mechanism. The MAR assumption will be verified in the sensitivity analysis (see handling missing data in quantitative analyses). Distributions of outcomes and key covariates over time will also be visually examined to identify systematic departures from normality and overall pattern over time, assisting us in evaluating the distribution of data and determining if assumptions are met for subsequent modeling approaches. We will conduct statistical analysis on transformed outcomes using Box Cox- or log-transformation to address any asymmetry.

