Given our study Aim 2 to understand how TEAM and TECH provide different benefits to individuals with different characteristics, we will explore potential heterogeneity of treatment effects in clinical response between subgroups of patients defined using patients' baseline characteristics. All co-variates will be identified a-priori. For Aim 2.a, we will examine whether and how the effect of TEAM and TECH approaches on BH symptom severity varies between patients with a high level of IBD disease activity (HBI or UCAI score > 4) and patients with low disease activity (HBI or UCAI score <=4) at baseline. IBD disease activity and effect of TEAM and TECH approach will also be assessed using a recently developed, validated, and preferred measure of disease activity for Crohn's disease and UC (PRO-2). 63,64 For statistical inference, we will fit the same GLMMs as described in Aim 1 and will include the higher order interaction terms with subgroups of patients defined by IBD activity. The null hypothesis of homogenous treatment effect between patients with high and low IBD activity in each outcome will be examined via interaction analysis (three-way interaction of time, treatment, and subgroup of IBD severity; two-way interaction of treatment and subgroup of IBD severity in the absence of a significant three-way interaction effect) using Wald test based on either F-distribution or Chisquare distribution as appropriate at the significance level of 0.05. In the presence of statistically significant treatment heterogeneity, the score change in BH symptom severity from baseline to each time point and their difference between TEAM and TECH will be estimated with 95% confidence intervals for subgroup of patients defined by IBD severity. For Aim 2.b, we will explore whether and how the effect of TEAM and TECH approaches on primary outcomes varies between young (age<=30) and older (age>30) patients. We will also examine the impact of TEAM and TECH on patients with differing IBD diagnoses, namely ulcerative colitis and Crohn's disease. Further, we will explore the effect of site differences, behavioral health history, insurance type (public vs. not), e-health literacy, and medications on response to TEAM or TECH intervention as secondary and exploratory analyses. For statistical inference, the same hypothesis test and statistical model described in Aim 2.a will be used. We will make a Bonferroni correction for multiple testing in order to conduct subgroup analyses at the overall significance level of 0.05. In the presence of statistically significant treatment heterogeneity,

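### Aim 2 interaction tests: Holm's step-down procedure would hold the same overall 0.05 as the planned single-step Bonferroni correction, never lose a rejection, and sometimes gain one

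*Combined protocol and SAP*

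**What the plan says.** In Quantitative Analysis, the Aim 2.a test of whether the treatment effect differs by baseline IBD activity uses a Wald test, with the reference "distribution as appropriate at the significance level of 0.05". The same model and test are then applied to age (Aim 2.b), IBD diagnosis, site, behavioral health history, insurance type, e-health literacy and medications. The paragraph adds: "We will make a Bonferroni correction for multiple testing in order to conduct subgroup analyses at the overall significance level of 0.05". It names no step-down procedure. It also does not say how many tests the correction covers, or whether the Aim 2.a test is one of them.

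The Aims section names two primary moderators, baseline IBD activity and age, and treats site, diagnosis and health literacy as secondary. Where heterogeneity is found, subgroup estimates are to be given with plain 95% confidence intervals.

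On power, Sample Size and Power Calculations says of the treatment-by-moderator interaction: "we expect 0.80 power to detect a significant interaction when the magnitude of B3 is at least 0.50". That statement does not mention the Bonferroni correction.

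**The concern.** Single-step Bonferroni holds each of k tests to 0.05/k, whatever the other tests show. Holm's procedure compares the smallest p-value with 0.05/k, the next with 0.05/(k-1), and so on, stopping at the first failure. Once one moderator is established, the next faces a less strict threshold, and the overall error is still held at 0.05.

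This matters because Aim 2 states a hypothesis for each of two primary moderators, so confirming both is the result it seeks. The plan claims no more than 0.80 power for one interaction, so there is little power to give away. The usual practical reason for keeping Bonferroni is that it yields simple simultaneous confidence intervals, and the plan does not use them.

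**Working it through.** **Inputs.** From Sample Size and Power Calculations: "considering 25% attrition, a sample size of 505 (approximately 252 per treatment group"; treatment and moderator independent, with the instruction "to simulate the binary moderator (M) and treatment (X) (both p=0.5"; residual SD 1; B3 = 0.50. Two-sided testing is an assumption: the plan says "Two-sided Wald T-test or Wald F-test" for the baseline comparisons but does not repeat it for the interaction tests. The number of tests m is not given, so a range is shown.

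**Step 1: reproduce the plan's figure.** In a balanced 2×2 layout each cell holds N/4 participants. Hence Var(B3) = 4 × 1/(N/4) = 16/N and SE = 4/√505 = 0.178. The standardised effect is 0.50/0.178 = 2.809. At two-sided 0.05, power = Φ(2.809 − 1.960) = 0.802, which matches the stated 0.80. So 0.80 is the power before any correction.

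**Step 2: power at the Bonferroni level.** Power = Φ(2.809 − z), with z taken at 1 − 0.05/(2m).

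| m | alpha per test | power |
|---|---|---|
| 2 | 0.025 | 0.715 |
| 3 | 0.0167 | 0.661 |
| 4 | 0.0125 | 0.622 |
| 8 | 0.00625 | 0.530 |

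The row m = 8 counts every moderator listed in Quantitative Analysis once.

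**Step 3: Holm with two independent tests, both real.** Write a = 0.7149 (power at 0.025) and b = 0.8021 (power at 0.05), so b − a = 0.0872.
- A given interaction is confirmed if its p-value is at most 0.025, or lies between 0.025 and 0.05 while the other is at most 0.025. Power = 0.7149 + 0.0872 × 0.7149 = 0.777.
- Both confirmed: Bonferroni 0.7149² = 0.511; Holm 0.8021² − 0.0872² = 0.636.
- At least one confirmed: 1 − (1 − 0.7149)² = 0.919 under both, because Holm's first step is the Bonferroni step.

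**Step 4: Holm with two tests, only one real.** The gain is 0.0872 × 0.025 = 0.002, or about 0.2 percentage points.

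**Step 5: wider families.** From simulation with 400,000 replicates per setting, power per real interaction:

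| m | real | correlation of test statistics | Bonferroni | Holm |
|---|---|---|---|---|
| 2 | 2 | 0.5 | 0.715 | 0.767 |
| 3 | 2 | 0 | 0.661 | 0.698 |
| 4 | 2 | 0 | 0.622 | 0.648 |
| 4 | 4 | 0 | 0.622 | 0.730 |
| 8 | 1 | 0 | 0.531 | 0.532 |
| 8 | 2 | 0 | 0.530 | 0.540 |
| 8 | 8 | 0 | 0.530 | 0.647 |

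**Step 6: error control.** Suppose m0 of the null hypotheses are true. Holm can make a false rejection only if the smallest p-value among those m0 is at most 0.05/m0. That has probability at most m0 × 0.05/m0 = 0.05, whatever the dependence. In the simulations Holm's family-wise error did not exceed 0.050 in any setting.

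**The case against.** **This is a preference between valid methods.** True. Bonferroni keeps the overall 0.05 and leads to no false conclusion. A reader might infer that the plan is in error here; nothing in the documents supports that.

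**The 0.715 to 0.777 gain is a favourable case.** Also true. It needs a family of two, both interactions real at B3 = 0.50, and independent tests. The plan offers 0.50 as a detectable effect, not an expected one. At an illustrative B3 = 0.25 (an assumption; standardised effect 1.404), power is 0.201 at 0.025 and 0.289 at 0.05. Holm then gives 0.201 + 0.088 × 0.201 = 0.219, a gain of under 2 points. The gain should be quoted only as a range.

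**Holm cannot be applied as the plan stands.** The family is undefined, and each moderator is tested in two stages: a three-way interaction, then a two-way one if the first is not significant. Both observations are correct, but they apply equally to Bonferroni, which also needs a family and one valid p-value per hypothesis. They are no reason to prefer Bonferroni.

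**The same gain for Aim 1.** A reader might extend the point to the two primary outcomes. The documents do not support this. The power section says only "After adjusting for the multiple testing in Aim 1 (2 tests", and the Aim 1 analysis text sets an overall 0.05; neither names Bonferroni. The plan also claims over 99.9% power for Aim 1, which on its own figure leaves nothing to gain.

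**Conclusion.** The point holds as an optional gain in efficiency for Aim 2 only. Holm dominates single-step Bonferroni for these tests, and nothing in the planned reporting is lost. With two real interactions of 0.50 and independent tests, the gain per interaction is about 6 points in a family of two, 2.6 points in a family of four and 1 point in a family of eight. With one real interaction it is negligible. It would be larger if most or all of the interactions in a wide family were real, which nothing in the documents suggests.

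A reader might infer that Holm makes good the power lost to the correction. It does not: the best two-test figure, 0.777, is still below 0.80, and the chance of finding any moderator at all is unchanged. That the stated 0.80 reproduces only at unadjusted 0.05 is a separate matter, which changing the procedure does not settle.

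These figures rest on the plan's single-outcome 2×2 model with normal errors and two-sided tests, not on the three-way interaction in the mixed model. The property that Holm keeps every Bonferroni rejection and the same error bound does not depend on that model, provided each hypothesis has one valid p-value.

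**What to change.** In the Aim 2 paragraph of Quantitative Analysis, replace the Bonferroni correction with Holm's step-down procedure at an overall two-sided 0.05. Name baseline IBD activity and age as the confirmatory family, in line with the primary moderators in the Aims section, and label the remaining moderators exploratory. State which outcomes each confirmatory moderator is tested on, since that sets the family size, and which p-value from the two-stage interaction test enters the procedure. Leave the 95% confidence intervals as planned, and make no change for Aim 1 on this account.

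The cost is a few sentences in the analysis plan, with no new data and no further participants. The family and the p-value have to be specified for Bonferroni as well, so naming Holm adds one phrase. The amendment should be dated before the statistician, who is masked to arm, sees results by arm.

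### The 0.80 power stated for an Aim 2 interaction of 0.50 assumes one test at 0.05, while the plan promises a Bonferroni correction over a number of tests it never states

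*Combined protocol and SAP*

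**What the plan says.** All references are to the Statistical Analysis Plan in the combined protocol and SAP, unless another section is named.

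- **Sample Size and Power Calculations, Aim 2.** For 505 analysed participants, "we expect 0.80 power to detect a significant interaction when the magnitude of B3 is at least 0.50". The figure comes from a simulation of a linear model with treatment, moderator and their product, set up "to simulate the binary moderator (M) and treatment (X) (both p=0.5" and with standard normal errors. No significance level and no multiplicity adjustment are given. The Aim 1 power statement, by contrast, says that it allows for two tests.
- **Quantitative Analysis, Aim 2.a.** The interaction of treatment with baseline IBD activity is tested on behavioral health (BH) symptom severity, "using Wald test based on either F-distribution or Chisquare distribution as appropriate at the significance level of 0.05". The statement of the null hypothesis refers more loosely to every outcome.
- **Quantitative Analysis, Aim 2.b and after.** Age (30 or under against over 30) is examined on the primary outcomes, of which there are two. IBD diagnosis follows. Then "we will explore the effect of site differences, behavioral health history, insurance type (public vs. not), e-health literacy, and medications", labelled secondary and exploratory, with the test and model of Aim 2.a carried over.
- **Quantitative Analysis, multiplicity.** After that list: "We will make a Bonferroni correction for multiple testing in order to conduct subgroup analyses at the overall significance level of 0.05".
- **Aims.** Aim 2 is one of three primary aims. IBD activity and age are its two primary moderators.

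**The concern.** The power section and the analysis section appear to use different significance levels for the same interaction tests. If the Bonferroni rule applies to them, each is judged at a level below 0.05 and the stated power does not apply. If Aim 2.a is exempt and kept at 0.05, the overall 0.05 does not cover all of the Aim 2 tests.

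Two consequences follow. A null moderator result under a primary aim would be read against a power that was calculated for a more lenient test. And with the number of tests left open, the threshold could be settled after results are known: it is 0.025 with 2 tests and about 0.003 with 16.

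**Working it through.** **Inputs.** From Sample Size and Power Calculations: N = 505 after attrition (675 × 0.75 = 506, so the plan's figure is consistent), treatment and moderator each split 50/50, residual SD 1, B3 = 0.50. From Quantitative Analysis: Wald tests on an F or chi-square distribution, hence two-sided. Assumption: the number of tests m, which the plan does not give, so a range is shown.

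**Formula.** In Y = B1·X + B2·M + B3·X·M + e, with X and M independent and each at 0.5:

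- SE(B3) = sqrt(16/N) = 4/sqrt(505) = 0.178
- B3/SE = 0.50/0.178 = 2.809
- Power = Φ(2.809 − z), where z is the two-sided critical value at 0.05/m
- B3 detectable with 0.80 power = (z + 0.842) × 0.178

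**The plan's own figure.** With m = 1, z = 1.960 and power = Φ(0.849) = 0.802, which matches the stated 0.80. A noncentral t calculation gives 0.801. A 42/58 moderator split, using the smallest subgroup share the plan expects, gives 0.792. A one-sided test at 0.05 gives 0.878 and does not match. A one-sided test corrected for two tests also gives 0.802, but the planned Wald tests are two-sided. The simulation used 100 runs, so its own standard error is sqrt(0.8 × 0.2/100) = 0.04; the closed form shows that the figure is sound for one test.

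**With the correction.**

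| m | What it would count | Level 0.05/m | z | Power at B3 = 0.50 | B3 for 0.80 power |
|---|---|---|---|---|---|
| 1 | one uncorrected test | 0.0500 | 1.960 | 0.802 | 0.50 |
| 2 | two primary moderators, one test each | 0.0250 | 2.241 | 0.715 | 0.55 |
| 3 | 2.a on BH severity, 2.b on both primary outcomes | 0.0167 | 2.394 | 0.661 | 0.58 |
| 4 | both primary moderators on both primary outcomes | 0.0125 | 2.498 | 0.622 | 0.59 |
| 8 | all eight named moderators, one test each | 0.0063 | 2.734 | 0.530 | 0.64 |
| 16 | eight moderators on two outcomes | 0.0031 | 2.955 | 0.442 | 0.68 |

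The eight moderators are IBD activity, age, IBD diagnosis and the five in the exploratory list.

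**If Aim 2.a stands outside the family.** Its 0.80 survives on this model. Aim 2.b alone still places two primary outcomes under the correction, so m is at least 2 and its power is at most about 72%. One 2.a test at 0.05 plus a corrected family at 0.05 bounds the error rate across Aim 2 at 0.10, not 0.05.

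**Sample size for comparison.** N = 16 × ((z + 0.842)/0.50)² gives 609, 671 and 714 analysed participants for m = 2, 3 and 4, against the 505 planned.

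**The case against.** The strongest defence is that the plan contains no demonstrable error. The 0.80 is correct for the test it describes. The 0.05 is attached to Aim 2.a, and the Bonferroni sentence comes later, after Aim 2.b and the exploratory list, so 2.a may be meant to stand alone. The power section also separates subgroup analyses from formal tests of moderation, and the Bonferroni sentence names only the former.

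Much of this stands. A reader might infer a flat contradiction between the 0.05 for Aim 2.a and the overall 0.05; the text is ambiguous and does not prove one. But the sentence just before the list's end brings in the Aim 2.a interaction test for the later moderators, so confining the correction to within-subgroup comparisons is not the natural reading. And exempting 2.a does not rescue the power for 2.b.

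A reader might also infer that the plan's rule brings power down to a definite figure as low as 44%. It does not: the rule gives no number of tests, two tests give about 72%, and the 16-test count multiplies eight moderators by two outcomes. Five of those moderators are labelled secondary and exploratory, no outcome is named for them, site has three levels, and e-health literacy and medications have no stated coding. For the same reason, that exploratory tests use up the level available to Hypotheses 2a and 2b is a possibility the wording leaves open, not something the plan states.

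Finally, the percentages are not the power of the planned analysis, a longitudinal mixed model with a three-way and then a two-way interaction. The documents give no within-patient correlation from which to compute that. This limits the new figures and the stated 0.80 equally, since both rest on the same simplified model.

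**Conclusion.** The concern holds as a mismatch between the power statement and the multiplicity rule, together with an undefined family of tests. The stated power belongs to one uncorrected two-sided test. Under any Bonferroni family of two or more, it is not reached at B3 = 0.50: about 72%, 66% and 62% for 2, 3 and 4 tests, with 0.80 power only from B3 of 0.55, 0.58 and 0.59. The values of 53% and 44% apply only if the secondary and exploratory moderators are counted.

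These results assume the protocol's cross-sectional model, a 50/50 moderator split, unit residual SD, 505 analysed participants and two-sided tests. The count of 3 is the closest to the outcomes named for Aims 2.a and 2.b; the loose reference to every outcome under 2.a would make it 4, and the further assessment of disease activity by PRO-2 could add more. Because the Research Synopsis gives the end of enrolment as February 28, 2024, the sample cannot be enlarged; what can still be settled is the family and the honest power figure.

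**What to change.** Before unblinding, amend the Aim 2 text as follows.

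1. Define the Bonferroni family as the tests of the two primary moderators (IBD activity and age) on the primary outcomes named for each, and state its size.
2. Say whether Aim 2.a is inside the family. If it is, replace its stand-alone 0.05 with the corrected level. If it is not, limit the overall 0.05 claim to the tests it covers.
3. Keep the analyses labelled secondary and exploratory outside the family and report them as exploratory. Say where IBD diagnosis falls; the Aims section treats it as secondary.
4. Restate the power at the corrected level. For example: with 3 tests, 0.66 power at B3 = 0.50 and 0.80 power for B3 of at least 0.58. Note that this rests on the simplified model.

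The cost is wording and a less favourable stated power, with no new data. Taking the exploratory moderators out of the family also gives up any error control the present wording might be read to promise for them, so their results should carry no confirmatory claim.

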
estimation of score changes in each outcome and their difference between TEAM and TECH will be presented with 95% confidence intervals for each subgroup of patients.

In handling missing data in quantitative analyses, we will attempt to determine the reasons for missing data and dropouts. The MAR assumption will be examined by comparing baseline characteristics between participants with and without missing data and conducting sensitivity analysis by repeating the main analyses without participants with missing data. If we observe statistical evidence that data are not MAR, we will stratify the participants into subgroups that share the same missing data pattern and estimate the statistical model separately for each missing data pattern. The results of all missing data analyses will be presented, and the sensitivity of our inference to the assumptions and approaches will be included in the interpretation of results.

COVID Considerations for Aims 1-2: Of our 675 projected participants, 32 were enrolled and completed their 6-month/primary outcomes surveys before the beginning of the COVID-19 (i.e., prior to March 12, 2020); 211 are potentially COVID-confounded (i.e., enrolled prior to or during the acute phase of the pandemic and were followed during it), and 432 were enrolled in the post-COVID phase of the study (after June 2021). Primary analyses will focus on the full sample of N=675, controlling for whether the participant was COVID-confounded. In sensitivity analyses, we will include only participants enrolled during the post-COVID phase. Effect sizes from sensitivity analyses will be assessed to evaluate whether findings are similar to those from the primary analyses.

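### The checks meant to verify MAR cannot separate it from non-MAR, yet they decide whether the only analysis relaxing MAR is run, and that analysis lacks an identifying assumption and a pooling rule

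*Combined protocol and SAP*

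**What the plan says.** All of this is in the Statistical Analysis Plan, under Quantitative Analysis, unless stated otherwise.

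- The generalized linear mixed models are said to be consistent under MAR or MCAR, and "The MAR assumption will be verified in the sensitivity analysis".
- The paragraph on handling missing data names two checks. First: "The MAR assumption will be examined by comparing baseline characteristics between participants with and without missing data". Second, a "sensitivity analysis by repeating the main analyses without participants with missing data".
- The next step is conditional: "If we observe statistical evidence that data are not MAR, we will stratify the participants into subgroups that share the same missing data pattern". The plan would then "estimate the statistical model separately for each missing data pattern". It names no test or threshold for the evidence, and gives no weights and no assumption for patterns without follow-up data.
- The plan also undertakes to seek reasons for missing data and dropout and to present every missing-data analysis, and says that "the sensitivity of our inference to the assumptions and approaches will be included in the interpretation of results".
- The Aim 1 paragraph asks for score changes from baseline to each time point, and their TEAM-TECH difference, with 95% confidence intervals. Hypothesis 1 (Aims) concerns improvement within each arm.
- The primary time point appears to be 6 months, from the COVID paragraph: "32 were enrolled and completed their 6-month/primary outcomes surveys before the beginning of the COVID-19". Compensation for Participation also lists 12-month self-report measures.
- The sample size section allows for 25% attrition and does not tie it to a visit.

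**The concern.** The main model already tolerates MAR, provided that what drives missingness is in the model. The open question is therefore whether dropout depends on scores that were never seen. Neither check addresses that question. A baseline difference between participants with and without missing data is compatible with MAR, and the absence of one is compatible with non-MAR. A gap between the completers-only and all-data results can likewise arise under either mechanism. Making the only non-MAR analysis depend on such evidence means it can run when it is not needed and be skipped when it is.

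Two sets of estimates are exposed. Dropout related to unseen outcomes that differs by arm can bias the TEAM-TECH contrast. If it is equal in both arms, it can still bias the within-arm changes on which Hypothesis 1 rests, because randomization does not cancel it there. Contrast bias is then nil or small.

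**Working it through.** **Amount of missing data in the plan.** 675 x (1 - 0.25) = 506.25. Working per arm, 337 x 0.75 = 252.75, which is the plan's figure of about 252 per group and 505 in total. The plan's figure reproduces, and about 675 - 505 = 170 participants are expected to be lost.

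**Illustration of the trigger.** All inputs except the arm size and the 25% are assumptions.
- Baseline y0 ~ N(0,1); follow-up y1 = 0.6 y0 + 0.8 e, with e ~ N(0,1) independent of y0. Higher is worse, there is no true arm effect, and there are 337 per arm.
- logit P(missing) = a + b x driver, with a set to give 25% missing (the plan's attrition) or 15% (assumed for month 6).
- Flag: one baseline t-test at p < 0.05, because the plan names no test.
- Contrast (TECH minus TEAM): regression on arm and baseline in the observed data. Its standard error is about 0.07 SD.

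| Dropout | b per SD | Flagged | Contrast bias, 25% missing | Contrast bias, 15% missing |
|---|---|---|---|---|
| Driven by baseline, both arms (MAR) | 0.4 | about 99% (25%), 95% (15%) | 0.00 | 0.00 |
| TECH only, driven by e (non-MAR) | 0.2 | about 5% | -0.04 SD | -0.02 SD |
| as above | 0.4 | about 5% | -0.08 SD | -0.05 SD |
| as above | 0.8 | about 5% | -0.14 to -0.15 SD | -0.09 SD |

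The negative sign means that TECH looks better than it is, because its sicker participants are missing.

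**Equal dropout in both arms.** When it is driven by the whole unseen score (b = 0.2/0.4/0.8), the within-arm change is biased by -0.03/-0.06/-0.12 SD at 25% missing and -0.02/-0.04/-0.07 SD at 15%. At b = 0.8 and 25% missing, contrast bias is 0.00 with no true effect and about 0.03 SD in size with a true effect of 0.5 SD. When dropout is driven by e alone, contrast bias is about 0.00 even with a 0.5 SD effect, while the within-arm bias is about -0.14 SD.

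**Completers-only check.** A separate three-visit illustration assumed correlations of 0.5 (baseline with month 6), 0.5 (baseline with month 12) and 0.6 (month 6 with month 12), and 25% missing at month 12. The mean absolute gap between the all-data and completers-only contrasts was 0.051 SD when MAR held (dropout on the 6-month score, opposite in direction by arm, slope 1.2; all-data bias about 0.00). It was 0.051-0.052 SD when MAR failed (dropout on the part of the 12-month score independent of baseline, opposite by arm, slope 0.6; all-data bias about 0.19 SD in size). The same gap arises under both mechanisms.

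**Several baseline comparisons.** With 10 independent tests at 0.05 under MCAR, the chance of at least one flag is 1 - 0.95^10 = 40%. Flags become more frequent but no more informative.

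**If the pattern analysis is run.** Assume 15% missing by month 6 and 25% by month 12, with monotone dropout. Then 0.15 x 675 = about 101 participants have baseline data only. 0.25 x 675 = about 169 have no 12-month score, so about 169 - 101 = 68 were seen only to month 6. A model fitted within the first pattern cannot estimate any change, and one fitted within the second cannot estimate 12-month change, unless an assumption is added.

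**Scale, in delta terms.** If a proportion p is missing in each arm and the missing values are shifted by arm-specific amounts, the contrast moves by p x (delta_TECH - delta_TEAM). At p = 0.25, a difference of 0.2 SD gives 0.05 SD, and 0.5 SD gives 0.125 SD. The prior behavioral effect sizes in the sample size section differ by .49 - .36 = 0.13. Moving the contrast that far needs a delta difference of 0.13/0.25 = 0.52 SD at 25% missing, or 0.13/0.15 = 0.87 SD at 15%. The plan does not define the SD unit behind .49 and .36, so this comparison is loose.

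**The case against.** The plan does more than many. It seeks reasons for dropout, names a pattern-based analysis, and promises to present all missing-data analyses and discuss sensitivity. These commitments have value. They do not make a non-MAR analysis unconditional, since an analysis that is never triggered cannot be presented.

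The sizes rest on assumed inputs and a simplified model. This stands. The planned model is longitudinal. Where a 6-month score is observed, the largest contrast bias for 12-month dropout falls from 0.14 to 0.12/0.11/0.08 SD at an assumed 6-to-12-month correlation of 0.6/0.7/0.8. The driver independent of baseline is the hardest to detect. TECH-only dropout driven by the whole unseen score at b = 0.8 was flagged in 68% (25% missing) or 54% (15%) of pooled comparisons. But harmless baseline-driven dropout is flagged even more often, so a flag does not identify the mechanism.

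A reader might infer more than the documents support:
- *That the trial's dropout is non-MAR, or that its results are biased.* Nothing in the documents shows this.
- *That the non-MAR analysis will not run.* It may well run; the trigger is uninformative rather than closed.
- *That equal dropout must bias the contrast whenever there is a true effect.* It depends on the driver, and the contrast bias found was at most about 0.03 SD.
- *That the false-positive rate would exceed one half.* About 52-56% appears only in the most extreme case (b = 0.8, 25% missing) at 0.05 per outcome. The sample size section adjusts for two tests; at 0.025 the rate is about 43-45%.
- *That the Aim 1 paragraph demands a single TEAM-TECH difference.* It asks for differences at each time point, in the main analysis. The missing pooling rule is a gap in the sensitivity analysis, not a breach of that paragraph.

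**Conclusion.** The point holds on the plan's own text and needs no simulation. MAR cannot be verified from observed data, and the only analysis that relaxes it depends on evidence that cannot bear on the question. That analysis is also incomplete, with no identifying assumption for participants lacking follow-up and no rule for combining patterns into an overall TEAM-TECH difference at each time point.

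The possible consequence is moderate. Under the assumed inputs, undetected arm-specific dropout biases the contrast by about one standard error or less at log-odds 0.2-0.4 per SD, and by about 0.09 SD (15% missing) to 0.15 SD (25% missing) at 0.8. These figures depend on the assumed correlation, slopes and single follow-up; the non-identifiability does not. The plan should be corrected, but the design is not invalidated.

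**What to change.** 1. Replace the statement that MAR will be verified with one saying that it cannot be tested from the observed data.
2. Keep the baseline comparison and the completers-only repeat, labelled as descriptive.
3. Remove the condition that statistical evidence must first be observed.
4. For both primary outcomes, always run a non-MAR sensitivity analysis, fixed before unmasking. Report the TEAM-TECH difference and the two within-arm changes at 6 and 12 months. Either form would serve: arm-specific delta-adjusted multiple imputation with a tipping point over a range that the sponsor justifies, or the plan's own pattern-mixture model with stated identifying restrictions and pattern-share weights.

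The cost is SAP wording, modest programming and one extra table, with no new data. The table may show that the conclusion is sensitive to missing data. It shows sensitivity to assumptions and does not detect non-MAR dropout. Fixing it in advance also matters because the plan labels analyses outside its a priori plan as ad hoc.
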